9. ASSESSMENTS

Please also see Schedule of Events table in Appendix 2.

9.1. Registration Assessments

Patients must give written informed consent **before** any trial specific screening investigations may be carried out. The following assessments or procedures are required to evaluate the suitability of patients for the trial and should be performed within 28 days prior to full registration unless otherwise stated:

- Complete medical history including demographics (including age and sex) and prior treatments
 - Medical history should include disease diagnosis, β 2-microglobulin levels at diagnosis, MYD88/CXCR4 status (if available), documenting relevant medical conditions
- Clinical examination: physical examination (including assessment of lymph node, liver and spleen size)
- Concurrent medication assessment
- Baseline adverse event assessment
- Observations: pulse, temperature, blood pressure, oxygen saturations
- Height and Weight
- Assessment of ECOG performance status (see appendix 3)
- Quality of life questionnaire – EORTC QLQ-C30 (to be completed before starting treatment)
- Full blood count (including red blood cell (RBC), haemoglobin (Hb), white blood cell (WBC) absolute neutrophil count (ANC), absolute lymphocyte count (ALC), haematocrit and platelets)
- Biochemistry (including bicarbonate, uric acid, albumin, alkaline phosphatase (ALP), alanine/aspartate transaminase (ALT/AST), total bilirubin, calcium, creatinine, potassium, sodium, glucose, urea, and estimated glomerular filtration rate (eGFR), U&E, liver function tests (LFT), LDH and amylase)
- Hepatitis B & C serology (HBsAg, HBsAb, HBcAb and HCV antibody) and HIV serology (note if HBcAb is positive HBV DNA testing will need to be performed)
- Electrocardiogram (ECG)
- Serum IgM, IgG and IgA
- Serum paraprotein
- Serum free light chain (SFLC)
- Direct antiglobulin test
- β 2 microglobulin
- TSH, glucose and ACTH tests
- Highly sensitive urine or serum pregnancy test in women of childbearing potential (WOCBP)
- CT scan of neck, chest, abdomen and pelvis (NCAP) (within 28 days prior to starting trial treatment)
- Bone marrow aspirate and trephine (within 28 days prior to starting treatment).

Research samples (see section 10 for further details) – all samples below are optional and therefore should only be obtained from patients who have given consent, been pre-registered and assigned a trial number

- Bone marrow aspirate and trephine
- Peripheral blood
- Lymph node biopsy (if nodal disease) to be obtained within 28 days prior to the start of treatment
 - If it is not possible to obtain a biopsy within 28 days prior to start of treatment, then historical biopsy tissue may be retrieved and sent to HMDS.

9.2. Assessments during Treatment

Patients should be seen prior to and during each cycle of trial treatment. Investigations should be performed in line with the Schedule of Events table in appendix 2.

9.2.1. Assessments prior to each cycle of treatment

The following assessments should be performed within 3 days prior to each cycle:

- Clinical examination: physical examination (including assessment of lymph node, liver and spleen size)
- Concurrent medication assessment
- Adverse event assessment
- Observations: pulse, temperature, blood pressure, oxygen saturations
- Weight
- Assessment of ECOG performance status (see appendix 3)
- Full blood count (including red blood cell (RBC), haemoglobin (Hb), white blood cell (WBC) absolute neutrophil count (ANC), absolute lymphocyte count (ALC), haematocrit and platelets)
- Biochemistry (including bicarbonate, uric acid, albumin, alkaline phosphatase (ALP), alanine/aspartate transaminase (ALT/AST), total bilirubin, calcium, creatinine, potassium, sodium, glucose, urea, and estimated glomerular filtration rate (eGFR), U&E, liver function tests (LFT), and amylase)
- Electrocardiogram (ECG)
- Serum IgM, IgG and IgA
- Serum paraprotein
- Serum immunofixation (only to be performed if paraprotein not detectable)
- TSH, glucose and ACTH tests
- Highly sensitive urine or serum pregnancy test in women of childbearing potential (WOCBP)

9.2.2. Disease response assessments

In addition to the assessments before each treatment cycle (section 9.2.1), disease response is to be assessed at 12 weeks (+/- 3 days), 24 weeks (+/- 3 days) and 1 year (+/- 2 weeks) after commencing treatment. The following assessments should be performed at these time points:

- Concurrent medication assessment
- Adverse event assessment
- Full blood count (including red blood cell (RBC), haemoglobin (Hb), white blood cell (WBC) absolute neutrophil count (ANC), absolute lymphocyte count (ALC), haematocrit and platelets)
- Biochemistry (including bicarbonate, uric acid, albumin, alkaline phosphatase (ALP), alanine/aspartate transaminase (ALT/AST), total bilirubin, calcium, creatinine, potassium, sodium, glucose, urea, and estimated glomerular filtration rate (eGFR), U&E, liver function tests (LFT))
- Quality of life questionnaire – EORTC QLQ-C30 (only performed at week 24)
- Serum IgM, IgG and IgA
- Serum paraprotein
- Serum free light chain (SFLC)
- Serum immunofixation (only to be performed if paraprotein not detectable)
- CT scan of neck, chest, abdomen and pelvis (NCAP) (CT scans to be performed at week 24 and 1 year after commencing treatment in patients with evidence of measurable/nodal disease on baseline scan)
- Bone marrow aspirate and trephine (only to be performed at week 24 and year 1 after commencing treatment).

Research samples – week 24 and 1 year only (see section 10 for further details) – all samples below are optional and therefore should only be obtained from patients who have given consent

- Bone marrow aspirate
- Peripheral blood

Response at these time points should be assessed using the International Working Group for WM response criteria (see appendix 4).

Patients will remain on treatment for a maximum of 1 year or until disease progression, discontinuation due to unacceptable toxicity or any other reason (whichever occurs sooner).

9.3. Assessments after Disease Progression

Following disease progression patients will be assessed at 5 months (+4 weeks) after the date of treatment discontinuation, over the phone or at a standard hospital visit for the purposes of:

- Adverse event assessment

Patients are then followed up for the trial annually from the date of progression for the following:

- Remission status assessment (investigations as per local protocols)

9.4. Assessments after treatment discontinuation (for reasons other than disease progression)

If patients complete treatment or are withdrawn from trial treatment early, for reasons other than disease progression the following assessments are to be performed on day 60 (+/- 3 days) following treatment discontinuation:

- Clinical examination: physical examination (including assessment of lymph node, liver and spleen size)
- Concurrent medication assessment
- Adverse event assessment
- Blood pressure
- Weight
- Assessment of ECOG performance status (see appendix 3)
- Full blood count (including red blood cell (RBC), haemoglobin (Hb), white blood cell (WBC) absolute neutrophil count (ANC), absolute lymphocyte count (ALC), haematocrit and platelets)
- Biochemistry (including bicarbonate, uric acid, albumin, alkaline phosphatase (ALP), alanine/aspartate transaminase (ALT/AST), total bilirubin, calcium, creatinine, potassium, sodium, glucose, urea, and estimated glomerular filtration rate (eGFR), U&E, liver function tests (LFT), LDH, and amylase)
- TSH, glucose and ACTH tests

Patients will then be assessed at 5 months (+4 weeks) after the date of treatment discontinuation, over the phone or at a standard hospital visit for the purposes of:

- Adverse event assessment

Patients are then followed up for the trial annually from the date of treatment discontinuation for the following:

- Remission status assessment (investigations as per local protocols)

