2.1.2. Clinical need in WM

Current treatment strategies include single agent rituximab or rituximab combination approaches. In the upfront setting, both Bendamustine plus rituximab, and Dexamethasone, cyclophosphamide and rituximab have shown to be effective approaches (Rummel et al, 2013; Kastritis et al, 2015). Proteasome inhibitor combinations with rituximab have also been studied in both the upfront and relapse setting (Gavriatopoulou et al, 2017; Treon et al, 2014).

Treatment at relapse is less standardised, however patients generally remain responsive to therapy, including rituximab combination approaches. Responses appear less durable with a median progression free survival (PFS) of 16-24 months, up until the advent of ibrutinib, which appears to give better results, with a median PFS of at least 4 years (Treon et al, 2015 Treon et al, 2017). There is now also evidence for combining rituximab with ibrutinib in the upfront and relapsed setting, and emerging data on small numbers of patients who have been treated with ibrutinib in the upfront setting (Dimopoulos et al, 2018; Treon et al 2018). However, relapse is inevitable and there is therefore a need for more effective drugs/combinations that can induce deeper and more durable responses, especially as there are some concerns about the nature and tempo of relapses following discontinuation/progression after ibrutinib (Gustine et al, 2017).

The need for recurrent treatment, the advanced median age at diagnosis, and the underlying biology of the condition, means that there is a relatively high rate of treatment-related complications, including infection, secondary malignancy and myelosuppression. Therefore the further development of chemotherapy-free regimes is attractive, and logical partners for combination therapy would include rituximab and ibrutinib.

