3. TRIAL DESIGN

This is a phase II, non-randomised, single arm, open label study to determine the safety, tolerability and efficacy (assessed by response rate) of pembrolizumab in combination with rituximab for the treatment of relapsed/refractory WM.

Patients with relapsed/refractory WM meeting the eligibility criteria will be recruited to the study. Patients will be treated on a 3 weekly cycle with the following:

- Rituximab 375mg/m² IV infusion on days 1, 8 and 15 for cycle 1
- Rituximab 375mg/m² IV infusion day 1 of cycle 2, then
- Rituximab 375mg/m² IV infusion given 12 weekly for a further 4 doses (total duration of rituximab treatment is 1 year)
- Pembrolizumab 200mg IV infused on day 2 of cycle 1, and day 1 of subsequent cycles for a maximum of 18 cycles (1 year) or until disease progression, discontinuation due to toxicity or any other cause (whichever occurs sooner)

Patients will be assessed for disease response (by serum IgM measurement) at 12 and 24 weeks post commencing treatment and at 1 year.

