12.2.1. Reporting of Adverse Events (AEs)

All adverse events that occur between informed consent and 5 months post last IMP administration must be recorded in the patient medical notes and the trial CRFs.

An AE cover sheet should be completed and a photocopy submitted to UCL CTC at each trial visit. The Adverse Event form should be submitted when there are new AEs or changes to existing AEs on the form. Any updates or changes to previously reported AEs must be initialed and dated. Report the worst grade observed for the AE on the form.

Those meeting the definition of a Serious Adverse Event (SAE) or Adverse Event of Special Interest (AESI) must also be reported to UCL CTC using the trial specific SAE Report. Also refer to section 12.2.2 (Reporting of Serious Adverse Events (SAEs)) and section 12.4 (Adverse Events of Special Interest)). Adverse events meeting the definition of an Urgent Event must be reported on an Urgent Event form (see section 12.5 Urgent Events).

Pre-existing conditions (i.e. conditions present at registration) do not qualify as adverse events unless they worsen or recur (i.e. improves/resolves and then worsens/reappears again).

E.g. an AE could be an exacerbation of a chronic or intermittent pre-existing condition including either an increase in frequency and/or intensity of the condition (worsening of the event). Another example of an AE is when a pre-existing condition improves during the trial (e.g. from grade 3 to grade 1) and then it worsens again (e.g. from grade 1 to grade 2), even if the event is of severity equal or lower to the original condition (improvement and recurrence of the event).

NB the disease(s) under study and its anticipated day-to-day fluctuations would not be an AE.

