17. STATISTICS

17.1. Sample Size Calculation

The primary endpoint is the overall response rate (defined as complete response (CR), very good partial response (VGPR), partial response (PR) or minor response (MR) i.e. a greater than 25% reduction in the serum IgM level) by 24 weeks post commencing treatment.

It is thought the response rate could be around 60% but a rate of more than 40% is needed for this combination to be taken forward into a larger study. Using an A'Hern phase II trial design with a 1-sided alpha of 0.05 and power of 80% we will require 42 patients. The primary endpoint will be met if we see 23 or more responses.

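### Patients who stop for progression have no scheduled safety bloods after discontinuation, so detection of late laboratory-only toxicity depends on the reason for stopping

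*Combined protocol and SAP*

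**What the plan says.** Section 9.4 covers patients who complete treatment or are withdrawn early, and states: "for reasons other than disease progression the following assessments are to be performed on day 60 (+/- 3 days) following treatment discontinuation". The list includes examination, adverse event assessment, full blood count, biochemistry with liver function tests, LDH and amylase, and TSH, glucose and ACTH. Footnote b of Appendix 1 repeats the restriction to patients who have not progressed.

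Section 9.3 covers the rest: "Following disease progression patients will be assessed at 5 months (+4 weeks) after the date of treatment discontinuation, over the phone". A routine clinic attendance is allowed in place of the call. The only purpose given is adverse event assessment. Annual remission status follows, by local protocols. No safety blood test is listed.

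The collection rules make no such distinction:

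- Section 12.2.1: "All adverse events that occur between informed consent and 5 months post last IMP administration must be recorded".
- Section 12.4 collects events of special interest up to 5 months after the last dose. One is defined entirely by simultaneous AST/ALT, bilirubin and alkaline phosphatase values.
- Section 17.2.2, first adverse event analysis, counts each patient's worst grade over all time points, with no split by reason for stopping.

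Before each cycle, section 9.2.1 requires full blood count, biochemistry with liver function tests, amylase, TSH, glucose, ACTH and IgM within 3 days of dosing.

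**The concern.** One adverse event rate is built from two groups with different surveillance after treatment, and what separates them is the efficacy outcome. Several immune-related events in section 8.4.2 are recognised wholly or partly from blood results: raised AST/ALT or bilirubin, thyroid disorders, nephritis and hyperglycaemia. A telephone call cannot detect the liver event of special interest.

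The bias has one direction. A progressor who was not tested enters the any-time table and the special-interest listing in the same way as a patient who was tested and found normal, so late laboratory toxicity tends to be under-counted in progressors. Safety is in the trial title and is the first-listed secondary endpoint. The plan already treats a day-60 panel as worth having for other patients, and it gives no reason for omitting it here.

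**Working it through.** **Plan's own figure.** The documents state no expected share of patients stopping for progression. The figure used below is the sample size. Section 17.1 gives "with a 1-sided alpha of 0.05 and power of 80% we will require 42 patients", with success defined as 23 or more responses. Exact binomial calculation with response rates of 40% and 60% gives a one-sided alpha of 0.0375 and power of 0.803 for 23 of 42, and 42 is the smallest size meeting both limits. The design is reproduced, so 42 is a sound denominator.

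**Inputs for the share without a day-60 visit**

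- Treatment period: section 3 gives pembrolizumab on "day 1 of subsequent cycles for a maximum of 18 cycles (1 year) or until disease progression". Use 12 months.
- Median PFS: section 2.1.2 says "Responses appear less durable with a median progression free survival (PFS) of 16-24 months" and gives at least 4 years (48 months) with ibrutinib. These are background figures, not design assumptions.
- Assumption: exponential PFS.

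**Formula.** Share progressing within 12 months = 1 − 0.5^(12 / median).

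| Median PFS (months) | Calculation | Share | Of 42 |
|---|---|---|---|
| 16 | 1 − 0.5^0.75 | 40.5% | 17.0 |
| 20 | 1 − 0.5^0.60 | 34.0% | 14.3 |
| 24 | 1 − 0.5^0.50 | 29.3% | 12.3 |
| 48 | 1 − 0.5^0.25 | 15.9% | 6.7 |

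The range is about 16% to 41%, or 7 to 17 patients. Counting only to day 1 of cycle 18 (51 weeks, about 11.73 months) changes it little: 15.6% to 39.8%. The formula counts deaths as progression and ignores patients who stop earlier for toxicity or by choice (who do have the day-60 visit), so it overstates the share somewhat.

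**Events that could be missed.** Let q be the probability of a late event detectable only by a laboratory test. The documents give no value, so q = 2% to 10% is assumed, with no pick-up in routine care. Missed events = patients without the visit × q.

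- Low end, median 24 months: 12.3 × 0.02 = 0.2 patients.
- High end, median 16 months: 17.0 × 0.10 = 1.7 patients.
- As a share of 42: 0.293 × 2% = 0.6 to 0.405 × 10% = 4.1 percentage points of the any-time rate.
- With the 48-month median: 6.7 × 0.02 = 0.13 to 6.7 × 0.10 = 0.67 patients.

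**Which analyses are exposed.** In section 17.2.2 the any-time worst-grade table and the reporting of events of special interest are clearly affected. The other three adverse event analyses are organised by treatment cycle and are largely untouched.

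**The case against.** **No blood test at all after the last dose?** A reader might infer this for progressors. The documents do not support it. Under section 9.2.1 a full panel, including IgM, falls due before each cycle. If a rise in IgM is found there and the next dose is not given, that panel is a safety test about 3 weeks after what becomes the last dose. Appendix 3 also asks for a confirmatory IgM measurement, although that is not a safety panel. The 12-week, 24-week and 1-year response visits may add bloods, but section 9.2.2 sits under assessments during treatment, and it is unclear whether a progressed patient still attends. What remains is the period from the last pre-cycle panel to month 5.

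**Toxicity missed in 30% to 40% of patients?** This reading is also tempting and also wrong. That figure is roughly the share without the visit under the 16- to 24-month medians. Most of those patients will have no late event.

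**Existing safeguards.** Section 8.11 and Appendix 1 provide yearly late-toxicity follow-up for all patients. Both groups have the same 5-month contact. Adverse events found in routine care must be recorded, and serious ones reported within 24 hours. These reduce the loss. They do not make testing equal, because none of them schedules a blood test in the months after stopping.

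**Limited consequences.** All adverse event analysis is descriptive, no comparison of toxicity with response is planned, and the IDMC trigger in section 17.3 counts treatment-related deaths. No decision rule is distorted. Patients who have not progressed also have no scheduled bloods between day 60 and month 5, so one day-60 sample would not find every late event. Since therapy after progression lies outside the trial and can confound results, omitting a fixed panel is defensible. All of this stands, and it is why the point is minor.

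**Conclusion.** The asymmetry is real and appears in both the text and the schedule. After discontinuation for progression no safety laboratory test is scheduled by the protocol, whereas other patients have a day-60 panel, and both groups feed the same any-time adverse event rate and special-interest listing. Detection of late laboratory-only toxicity therefore depends on efficacy outcome, with bias towards under-counting in progressors.

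About 16% to 41% of patients (7 to 17 of 42) would lack the visit. This rests on exponential PFS and background medians, and ignores deaths and earlier stops for other reasons. The expected number of missed events is small: about 0.2 to 1.7 patients in the 29% to 41% case, resting on an assumed 2% to 10% late event rate and no pick-up in routine care. The severity is minor. The case for acting is that a cheap change would stop an untested patient being read as an event-free one.

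**What to change.** 1. In section 9.3 and Appendix 1 footnote b, have the existing day-60 form completed for every patient who stops, whatever the reason. For progressors, enter the available routine full blood count, biochemistry, TSH, glucose and ACTH results nearest day 60, their dates, and the start date of any new WM therapy.
2. In section 17.2.2, report post-treatment adverse events and events of special interest separately from on-treatment events, by reason for stopping, with the number of patients who had post-treatment bloods as denominator.

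This changes data capture and reporting only. It needs no extra visit and alters no treatment rule. The cost is a small wording change and one extra form per progressor, about 7 to 17 forms on the range above. TSH and ACTH will often be missing because routine care may not include them, and some results will be confounded by new therapy, which is why its start date must be shown. The change reduces the bias and makes it visible, but does not remove it.

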Duration of follow up:	Patients will be followed up for a minimum of 2 years post registration into the study
Definition of end of trial:	The end of trial will be declared when the final data item from the final patient is received (i.e. it is anticipated that this will be when the final patient completes their 2-year follow-up visit).

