8.11. Clinical Management after Treatment Discontinuation

After treatment discontinuation, further therapy will be at the discretion of the treating clinician. Subsequent treatment will not be considered part of the trial.

If a patient discontinues trial treatment early, they will remain on trial for follow up purposes unless they explicitly withdraw consent. Also refer to sections 9 (Assessments) and 15 (Withdrawal of Patients) for further details regarding treatment discontinuation, patient withdrawal from trial treatment and withdrawal of consent to data collection.

For all patients, disease status, late toxicity and survival will be followed up yearly until the last patient completes 2 years of follow up and the end of trial is declared.

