16. TRIAL CLOSURE

16.1. End of Trial

For regulatory purposes the end of the trial will be when the final data item for the final patient is received by the UCL CTC (i.e. it is anticipated that this will be when the final patient completes their 2 year follow-up visit). At this point the 'declaration of end of trial' form will be submitted to the MHRA and Ethics Committee, as required.

Following this, UCL CTC will advise sites on the procedure for closing the trial at the site.

Once the end of trial has been declared, no more prospective patient data will be collected but sites must co-operate with any data queries regarding existing data to allow for analysis and publication of results.

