Progression free survival will be analysed using Kaplan-Meier survival analyses, with the time calculated from the date of registration to the date of progression/death. Patients who are alive and progression free will be censored at the date last seen. The median (if applicable), rates at 1 and 2 years and a Kaplan-Meier curve will be presented.

Overall survival

Overall survival will be analysed using Kaplan-Meier survival analyses, with the time calculated from the date of registration to the date of death. Patients who are alive will be censored at the date last seen. The median (if applicable), rates at 1 and 2 years and a Kaplan-Meier curve will be presented.

Quality of life

Quality of life is assessed using the QLQ-30 questionnaire at baseline and at week 24. Differences between baseline and week 24 will be compared using paired t-tests and changes between baseline and week 24 may also be compared to historical data from the R2W trial.

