- d: Adverse events are to be recorded between informed consent and 5 months after the last IMP administration. AESI and SAES are to be reported to UCL CTC within 24 hours of awareness (see section 12 for details),
- e: A 12 lead ECG should be performed for all patients pre-registration and prior to commencing each cycle of pembrolizumab. Further ECGs should be performed as clinically indicated.
- f: Serum immunofixation to be performed only if paraprotein no longer detectable.
- g: CT scan of neck, chest, abdomen and pelvis (NCAP) to be performed pre-registration (within 28 days prior to starting treatment). CT scan (NCAP) to be repeated at 24 weeks and 1 year post commencing treatment only if nodal disease on baseline assessment. Thereafter, only to be done if clinical concerns of nodal progression. If no measurable disease was documented at baseline, then a CT NCAP should be performed as clinically indicated.
- h: Bone marrow aspirate and trephine to be performed pre-registration (within 28 days prior to starting treatment) and at week 24 and 1 year to determine response. Samples to be analysed locally. Additionally, for consenting patients bone marrow samples to be sent to HMDS for exploratory analysis (see section 10 for further details).
- i: Peripheral blood sample for MyD88 and CXCR4 analysis will be sent at screening to HMDS for exploratory analysis from consenting patients (see section 10 for further details).
- j: Peripheral blood sample for flow cytometry for B-cell/plasma cell phenotypes will be sent to HMDS for exploratory analysis from consenting patients (see section 10 for further details).
- k: Remission status as per local policy.

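### After treatment and the 1-year assessment, no scheduled visit explicitly requires serum IgM or paraprotein, and annual checks are timed from treatment discontinuation while 2-year PFS is timed from registration

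*Combined protocol and SAP*

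**What the plan says.** **Endpoint.** Section 17.2.2 analyses PFS by Kaplan-Meier, "with the time calculated from the date of registration to the date of progression/death", with rates at 1 and 2 years. Event-free patients are censored when last seen. Appendix 3 defines progression as an IgM rise of at least 25% from the nadir and/or clinical progression, and footnote a asks for IgM changes to be confirmed by a second measurement.

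**Tests on treatment.** IgM and paraprotein are required before each cycle (9.2.1) and at 12 weeks, 24 weeks and 1 year after starting treatment (9.2.2).

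**Tests afterwards (9.4 and Appendix 1).**
- Day 60 after discontinuation has an examination, blood count, biochemistry and endocrine tests, but not IgM or paraprotein.
- The 5-month contact covers adverse events only and may be by telephone.
- After that: "Patients are then followed up for the trial annually from the date of treatment discontinuation for the following" a remission status assessment. Footnote k of Appendix 1 adds "Remission status as per local policy".

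**Length of follow-up.** Section 1.1 says "Patients will be followed up for a minimum of 2 years post registration into the study". Section 8.11 says "disease status, late toxicity and survival will be followed up yearly until the last patient completes 2 years of follow up", without naming tests or visit dates. Section 16.1 ties the end of trial to the last patient's data, where "it is anticipated that this will be when the final patient completes their 2 year follow-up visit"; neither section 9 nor Appendix 1 contains such a visit.

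**The concern.** A progression can be dated only when someone looks for it. In year 2 the protocol does not explicitly require the measurement that most directly defines progression, and the only scheduled disease check may fall just after the landmark. A patient whose IgM rises in, say, month 17 without clinical signs, and whose rise is first found at a check after month 24, counts as progression-free in the 2-year rate. The full Kaplan-Meier curve would show a drop soon after month 24, but the quoted 2-year figure would not include it.

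Test frequency may also differ among the 10 planned sites, so the timing of detection would vary in a way that cannot be separated from the drug effect afterwards. Section 2.1.2 gives more durable responses as a reason for new combinations, and section 2.1.4 criticises non-standardised response measurement in other studies. The 2-year PFS rate is therefore likely to be read against other series.

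**Working it through.** The plan states no target or precision for PFS, so there is no PFS figure to reproduce. The one calculated design figure, success at 23 or more responses in 42 patients (17.1), does reproduce: exact one-sided alpha 0.0375 and power 0.803. It does not depend on this point.

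**1. Last required IgM and paraprotein.** In Appendix 1 the IgM row has five marks (pre-registration, day 1 of each cycle, 12 weeks, 24 weeks, 1 year). The blood count row has a sixth, for day 60. This agrees with 9.4.

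**2. Date of the first annual check for a completer.** Inputs: 18 three-weekly cycles (8.2); annual check counted from discontinuation (9.4).
- Discontinuation taken as the last dose: 17 × 21 = day 357 after first dose; 357 + 365 = day 722. Slack before two years: 730 − 722 = 8 days.
- Discontinuation taken as the end of cycle 18: 18 × 21 = 378; 378 + 365 = day 743, already past 730.

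The documents do not define the date. The first reading is the more natural, because the 5-month contact after discontinuation matches the adverse event period in 12.2.1: "All adverse events that occur between informed consent and 5 months post last IMP administration must be recorded".

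**3. What uses up the 8 days.** From registration, the check falls on day 722 + gap from registration to first dose + total delay. Under 8.3.2 a logistical delay may last up to 7 days, and one of more than 2 days shifts all later doses. Under 8.4.1 cycles delayed for adverse events are not omitted. A 2-day gap and one 7-day delay give 722 + 2 + 7 = day 731.

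**4. Early stoppers.** Stopping at month 6 without progression gives annual checks at about months 18 and 30, so months 18 to 24 have no scheduled check before the landmark. Section 3 and section 10 favour the 1-year IgM assessment still applying to these patients, but 9.4 does not list it.

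**5. Ceiling on the upward effect (illustration).** Assumptions: exponential PFS; every patient who does not progress completes treatment; last required IgM at month 12; no year-2 progression dated before month 24. Medians are from 2.1.2 (16 to 24 months at relapse, at least 4 years with ibrutinib). With S(t) = 2^(−t/median), apparent 2-year PFS equals S(12), and the excess is S(12) − S(24).

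| Median (months) | S(12) | S(24) | Excess, whole cohort |
|---|---|---|---|
| 16 | 59.5% | 35.4% | 24.1 points |
| 24 | 70.7% | 50.0% | 20.7 points |
| 48 | 84.1% | 70.7% | 13.4 points |

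If half of the year-2 progressions are dated on time, the excess halves to about 12, 10 and 7 points. If all are, it is 0. If the first annual check includes IgM and falls on day 722, the residual is 0.3 to 0.4 points.

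**6. Effect in the other direction.** Suppose progressions are reported promptly (12.5), but event-free patients are last seen at an annual check. At data cut, a month-6 stopper with less than 30 months of follow-up is censored at month 18 if event-free, yet contributes an event if progression occurs after month 18. Simulation assumptions: uniform recruitment over 27 months (1.1), data cut when the last patient reaches month 24 (16.1), exponential PFS. For month-6 stoppers, 2-year PFS comes out at about 43%, 57% and 75% against true values of 2^(−18/median) = 45.9%, 59.5% and 77.1%: about 2 points too low.

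**The case against.** **Remission status cannot be assigned without IgM.** Every category from complete response to stable disease in Appendix 3 rests on serum or monoclonal IgM, and 8.11 requires yearly disease status. On this view local practice chooses the test list, not the definition, and clinics seeing IgM-secreting disease will measure it. This has force and is why the excess may be near 0. It does not settle timing: the test is not listed, its frequency is not set, and the check can fall after the landmark.

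**Progression is an urgent event, reportable within 72 hours (12.5).** That clock starts when the site becomes aware of a locally confirmed progression. It does not require anyone to test.

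**Clinical progression can be seen without IgM.** True, for example at the day 60 examination. It does not cover progressions shown only by IgM.

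**PFS is secondary, single-arm and descriptive.** True. With 42 patients and a rate near 50%, the standard error is √(0.25/42), about 8 points. This limits the importance of the point, but sampling error does not excuse a bias that is cheap to remove.

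**Stronger readings that a reader might infer, and that the documents do not support.**
- *That the bias can only be upward.* Censoring at the date last seen with prompt event reporting can pull the other way (step 6).
- *That 24, 21 and 13 points estimate the bias, or apply within completers.* They are whole-cohort ceilings. Completers are progression-free to about month 12, so the ceiling within that subgroup is 1 − S(24)/S(12) = 41, 29 and 16 points. A trial-level estimate needs the completer fraction and local test frequency, and the documents give neither.
- *That the gap from registration to first dose is capped at 28 days.* The 28-day marrow window in 9.1 supports this only if registration means full registration and the marrow comes first. Section 17.2.2 does not say whether preliminary or full registration is meant.

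**Conclusion.** The schedule gap is real and worth closing as a cheap improvement. After the last pre-cycle test and the 1-year assessment, IgM and paraprotein are not explicitly required at any scheduled visit. The annual checks are also anchored to a different date from PFS, so a completer's first check sits at or just beyond the 2-year landmark and a month-6 stopper's second check sits about six months beyond it.

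The main risk is overstatement of 2-year PFS, with a smaller possible understatement among early stoppers. The net size cannot be determined from the documents. It ranges from near 0 with regular local testing to the whole-cohort ceiling of 24, 21 or 13 points at medians of 16, 24 or 48 months, which needs every assumption in step 5 to hold. Deaths are dated exactly, which lowers the ceiling.

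The 24-week response endpoint, the sample size and the success rule are not affected.

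**What to change.** 1. In 9.4 and Appendix 1, time the annual remission-status visits from registration, and require serum IgM and paraprotein at each. Include a 24-month visit scheduled to fall before the landmark. This also supplies the 2-year visit that 16.1 expects. State whether registration means preliminary or full registration.
2. Add IgM and paraprotein to the bloods already drawn at day 60.
3. State in 9.4 that the 1-year IgM assessment applies to patients who stopped early without progression.
4. In 17.2.2, state that a progression confirmed by a second IgM is dated at the first qualifying measurement. Otherwise a rise seen at the 24-month visit and confirmed later would move past the landmark.
5. Optional: a PFS sensitivity analysis with interval censoring between the last progression-free assessment and the detection date. A 24-month visit places an event before or after the landmark but does not date it within year 2; this analysis addresses that and needs only assessment dates.

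Cost: two assays on existing day 60 blood, one blood sample per annual visit, and some changed visit dates. Treatment, sample size and the primary analysis are unchanged.
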